1.1 SYNOPSIS

Title: Acupuncture Treatment for Chronic Post-traumatic Headache in

Individuals with Mild Traumatic Brain Injury.

IRB Number: A19-094

Study Description: The purpose of the study is to determine the effect of a low vs. high

dose of acupuncture treatment in individuals with chronic post-traumatic headache (CPTH). A total of 40 people with mild traumatic brain injury (mTBI) suffering from CPTH will be enrolled in this study to

receive acupuncture treatment for 5 weeks. Participants will be randomized into two groups: 1) Low Acupuncture group (5 treatments) and 2) High Acupuncture group (10 treatments). We hypothesize that both treatment groups will have decreased headaches, but that 10 treatments will greater alleviate headaches when compared to 5

treatments.

Specific Aims: Specific Aim 1: To determine the effect of a low versus high dose

acupuncture treatment on number of headache days for individuals

suffering from CPTH.

Specific Aim 2: To determine the safety and tolerability of acupuncture

on CPTH in individuals with mTBI.

Specific Aim 3: To explore the effects of acupuncture on sleep, quality of life (QOL), headache outcomes, and medications in individuals

with mTBI who suffer from CPTH.

Endpoints: Primary Endpoint: Number of headache days over 4 weeks

Secondary Endpoints: 1) Adverse or Serious Adverse Events and 2)

Completion of treatment durations and sessions

Exploratory Endpoints: 1) Sleep, 2) Quality of life, 3) Headache

Outcomes, and 4) Medications

Study Population: 40 individuals aged 18-70 with a diagnosis of mTBI suffering from CPTH

will be recruited for this study.

Description of

Sites/Facilities Enrolling

Participants:

Participants will be enrolled at HealthPartners Neuroscience Center, and will be treated at the Neuroscience Center, HealthPartners Clinic

St. Paul Como, or Healing Response Acupuncture & Functional

Neurology.

Description of Study
Intervention/Experimental

intervention, Experimenta

Manipulation:

Acupuncture treatment will be administered by a licensed

acupuncturist for a duration of 5 weeks. One treatment group will receive 5 treatments and the other will receive 10 treatments.

Study Duration: The duration of this study is 2 years.

Participant Duration: Participants should complete all study-related tasks within 176 days

(approximately 6 months).

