4 STUDY DESIGN

4.1 OVERALL DESIGN

Study Design:

This study is an unblinded, uncontrolled randomized, 2-arm clinical trial.

Hypotheses:

Primary Hypothesis: We hypothesize that both treatment groups will have decreased headaches. **Secondary Hypothesis:** We hypothesize that acupuncture will be safe and tolerated in both groups.

Randomization:

Prior to the first acupuncture treatment visit, participants will be randomized into two treatment groups. Randomization is explained in **Section 6.3**.

Acupuncture Treatment Groups:

Group 1: 18 participants will receive acupuncture treatment 1x per week for 5 weeks = 5 total. **Group 2:** 18 participants will receive acupuncture treatment 2x per week for 5 weeks = 10 total.

Study Intervention:

Acupuncture treatment will consist of a standardized treatment protocol designed for this study. Specifically, 18 needles will be inserted into specific areas of the body for a duration of 30 minutes. Additional details of the treatment are discussed in **Section 6.1**.

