6.5 CONCOMITANT THERAPY

For this protocol, participants may use non-opioid analgesics for pain control, including over-the-counter medications and dietary supplements, and prescribed medications. This includes use for rescue therapy in the event of exacerbation of symptoms due to acupuncture treatment. Medication usage will be assessed at each study visit and documented in the relevant eCRF.

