8 STUDY ASSESSMENTS AND PROCEDURES

8.1 ENDPOINT AND OTHER NON-SAFETY ASSESSMENTS

Demographics: Demographic information will be collected, including: gender, age, race, ethnicity, language, height, weight, marital status, employment status, date of TBI, date of CPTH diagnosis, and email address for Headache Diary surveys (discussed below).

Medication Review: Medication data will be used for exploratory purposes for Specific Aim 3.

Headache Diary: Participants will be sent an e-mail REDCap survey to complete and asked to record headache information for three 4-week time periods. During each 4-week period, they will receive the e-mail once per week. They will be provided paper headache diaries (Appendix 1-3) to keep track of their headaches and will be asked to complete each e-mail survey they receive. The headache diary survey will include: how many headaches occurred each week during the 4-week period, duration, pain intensity (0-10 scale), type (e.g. tension), and name of medication taken and dosage (if applicable). The outcome measure for Specific Aim 1 is number of headache days over 4 weeks; other variables will be exploratory.

Treatment Adherence: The participant's treatment adherence will be measured to determine tolerability of acupuncture. We will record the number of attended acupuncture sessions. We will also record participants' ability to maintain the acupuncture duration of 30 minutes per session.

Sleep: Participants will be asked to complete the Pittsburgh Sleep Quality Index (PSQI), which contains questions about one's usual sleep habits during the past month.

Quality of Life: Participants will be asked to complete the TBI-QOL short forms. The TBI-QOL includes the following domains: ability to participate in social roles and activities, anger, anxiety, attention-concentration, cognition-general concerns, communication, depression, emotional behavior dyscontrol, executive function, fatigue, grief-loss, headache pain, independence, learning-memory, mobility, pain interference, positive affect and well-being, resilience, satisfaction with social roles and activities, self-esteem, stigma, and upper extremity.

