9.4.9 EXPLORATORY ANALYSES

Exploratory outcomes (headache: intensity, duration, type; sleep; and QOL) will be compared between groups with Student's t-test, Chi-square test, and Mann-Whitney-U test and mixed-model ANOVAs, as appropriate. As an exploratory analysis, patients who report post-COVID-19 symptoms will be identified using the additional COVID-19 set of questions. Types and severity of post-COVID-19 symptoms present within the group will be described. The t-test or non-parametric equivalent will be used to determine whether acupuncture had an effect on post-COVID symptoms.

As some patients' medication adherence and regimens are expected to change throughout the intervention period, a sensitivity analysis will be performed for all primary and secondary endpoints in which we exclude patients with medication regimen ammendments. These results will be compared to our main analysis to help contextualize any observed intervention effect. Patients with and without changes to their medications during the trial will be described separately and any differences will be presented. If necessary, we will conduct a sensitivity analysis in which we exclude participants that had protocol deviations (e.g. large delays between treatments) due to illness, for example COVID-19.

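### The sensitivity analysis that excludes patients with medication changes cannot show whether the dose effect is robust, and medication use itself is missing from the planned between-arm comparisons

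*Combined protocol and SAP*

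**What the plan says.** Section 9.4.9 (Exploratory Analyses) gives the reason for the analysis, "As some patients' medication adherence and regimens are expected to change throughout the intervention period", and then commits to it: "a sensitivity analysis will be performed for all primary and secondary endpoints in which we exclude patients with medication regimen ammendments". Its purpose is stated next: "These results will be compared to our main analysis to help contextualize any observed intervention effect". The same paragraph promises a separate description of patients with and without medication changes. It does not define what counts as an amended regimen.

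Section 4.1 fixes the order of events: "Prior to the first acupuncture treatment visit, participants will be randomized into two treatment groups". Specific Aim 3 in the Synopsis treats medication as something the treatment may alter: "To explore the effects of acupuncture on sleep, quality of life (QOL), headache outcomes, and medications in individuals". Medications are also the fourth exploratory endpoint in Sections 3 and 9.1. The list of exploratory outcomes to be compared between groups in Section 9.4.9 names headache intensity, duration and type, sleep, and quality of life. Medication is not on it.

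On data capture, Section 6.5 states "Medication usage will be assessed at each study visit and documented in the relevant eCRF". Section 8.1 adds drug name and dosage to the headache diary in each of its three 4-week periods. On analgesics, Section 6.5 also says "This includes use for rescue therapy in the event of exacerbation of symptoms due to acupuncture treatment".

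**The concern.** A sensitivity analysis tests robustness only if it asks the same question of groups that are still comparable. This one selects patients on an event that follows randomisation and that the protocol itself lists as a possible effect of treatment. A patient who is not improving may add a drug, and a patient who is improving may stop one. If that happens, the rule removes people according to their outcome, and removes different people in each arm if dose matters.

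Two design features could make the selection uneven. Participants and staff know the assignment (Sections 4.2 and 6.3). Medication is also assessed at every visit, so the high-dose arm has 10 treatment visits at which a change can be noted and the low-dose arm has 5. An undefined term leaves room for unblinded staff to decide late who is excluded.

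What is at stake is interpretation. A smaller difference in the subset might be read as showing that medication explained the effect, and a similar one as reassurance. Neither reading follows. Meanwhile no between-arm comparison of medication use, which would inform the question directly, is named.

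**Working it through.** **Inputs from the documents.** 18 per arm, two-sided alpha 0.05, SD 4.47 (4.5 in the tables), difference 4.5 days (26 versus 21.5), stated power 0.835 (Section 9.2). The proportion of patients changing medication, and its link to response, are not given and are assumed below.

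**The plan's own figure.** For a two-sample t-test the noncentrality is δ / (σ√(2/n)) = 4.5 / (4.5 × √(2/18)) = 3.00 on 34 degrees of freedom, giving power 0.830. With σ = 4.47 the noncentrality is 3.02 and power is 0.835. The stated figure is reproduced.

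**Method.** Each patient's change in headache days, y, is drawn from a normal distribution. The patient is excluded with a probability that may depend on y, and the t-test is run on those retained. The estimate is the low-dose mean change minus the high-dose mean change, so a positive value favours 10 treatments.

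**Step-type assumptions, true difference 4.5.** Mean changes are 0 and −4.5, or −2.25 and −6.75. A non-improver is a patient with y above a cut-off of 0 or −2 days.

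| Assumed reason for exclusion | Estimate (days) | Kept of 36 | Power |
|---|---|---|---|
| Nobody excluded | 4.5 | 36 | 0.83 |
| 30% in each arm, unrelated to response | 4.5 | 25 | 0.66 |
| 30% low, 45% high, unrelated to response | 4.5 | 22.5 | 0.585 |
| Non-improvers 60%, others 10%, both arms | 3.8–4.1 | 24–29 | 0.58–0.66 |
| As above, strong responders also 60% | 3.0–3.3 | 21–25 | 0.45–0.51 |

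Moving the cut-offs stretches the last two rows to about 3.0 to 4.2 days and power of about 0.43 to 0.66. The third row shows that more frequent detection in one arm does not bias the estimate by itself. It matters only together with a link to response.

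**How much of the power loss is sample size.** In the non-improver scenario, removing the same number of patients at random already lowers power to 0.63–0.73. The fall from 0.83 is then 0.10 to 0.20 from numbers alone, out of 0.17 to 0.25 in total (0.83 − 0.66 and 0.83 − 0.58). More than half is lost sample size.

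**Scale of the shift.** The bias is 4.5 − 4.2 = 0.3 to 4.5 − 3.0 = 1.5 days. The standard error of the full-sample difference is 4.47 × √(2/18) = 1.49 days.

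**Smooth-link assumptions, true difference 4.5.** Mean changes are −2 and −6.5, SD 4.5. Escalation probability is 0.8 / (1 + exp(−(y+1)/1.5)). Tapering probability is 0.8 / (1 + exp((y+6)/1.5)). The weak escalation link is 0.15 + 0.3 / (1 + exp(−(y+1)/3)).

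- Weak escalation: 4.3 days, 27 kept, power 0.68.
- Strong escalation: 3.5 days, 28 kept, power 0.58.
- Tapering: 3.5 days, 25 kept, power 0.53.
- Escalation and tapering in both arms: 2.7 days, 17 kept, power 0.30.
- Low arm escalates, high arm tapers: 0.5 days, 22 kept, power 0.06.

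**No true difference.** The same mechanism in both arms gives a difference of 0 and rejection near 0.05. Step-type escalation in the low arm only makes that arm look 0.7 to 1.1 days better, with rejection in 7 to 10% of trials. Opposite mechanisms in the two arms give a false advantage for the low dose of 1.8 days with 21% rejections (step type), or about 3 days with 47% rejections (smooth link).

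**The case against.** The strongest reply is that the link to response is not in the documents. Section 9.4.9 says only that regimens and adherence are expected to change. Version 8.0 in the amendment history, which removed the stable-regimen criterion, cites participants' need for flexibility and not headache response. Rescue analgesic use is tied to symptoms in Section 6.5, but the plan does not say that it counts as a regimen amendment. A reader might infer that every change is a consequence of response. That is plausible, but it is not stated, and without the link the table shows no bias. This objection stands, so the point has to be conditional.

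The analysis is also secondary in status. Sections 9.3 and 9.4.2 keep the main comparison intention-to-treat, Section 9.4.9 is headed exploratory, and Section 9.4.3 rules out inferential statistics on the secondary endpoints. In inferential terms, the rule affects one further look at the primary endpoint. With the stable-regimen criterion gone, there is also a fair reason to want some analysis that addresses changing co-medication.

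Finally, part of any remedy is already planned: the main analysis ignores medication changes, and patients with and without changes will be described. What the plan lacks is that information by arm and by direction of change. None of this rescues the stated use. When the reasons for change are unknown, comparing the subset with the main analysis cannot separate a dose effect from selection.

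**Conclusion.** The concern holds as a conditional one. Excluding patients on a post-randomisation variable that the protocol lists as a possible treatment effect cannot serve as a robustness check, and the omission of medication from the between-group list is a real gap.

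The sizes rest on assumed change probabilities and illustrate rather than predict. Under the step-type assumptions a true 4.5-day difference is estimated at about 3.0 to 4.2 days with power of about 43 to 66%. Weaker or stronger links fall outside that range on either side. With no true difference, escalation in the low arm alone produces a false 0.7 to 1.1 days.

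Two stronger readings are tempting. One is that a real effect would seem to vanish, or a null effect would look convincingly real. That happened only when the low arm escalated and the high arm tapered, and nothing in the documents points to such opposite behaviour. The other is that the trial's main conclusion is compromised. It is not, because the primary comparison keeps patients regardless of medication change. This is an inexpensive improvement to the plan and not a threat to its primary result.

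**What to change.** 1. In Section 9.4.9, stop using the exclusion analysis to judge the robustness of the intervention effect. Either drop it, or keep it labelled as descriptive and non-causal.
2. If it is kept, define an amended regimen before the data are examined: which products count, whether a dose change or only a start or stop counts, over what period, and whether rescue use is included.
3. Add medication to the between-group exploratory comparisons. Among all randomised patients, report by arm the medication use in each 4-week diary period, and the proportions with regimen increased, decreased or unchanged.

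The cost is SAP wording and a few extra tables from data already collected at visits and in the diary. The downside is that the unchanged-medication subset no longer supports a causal reading, which it could not support in any case.

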10 SUPPORTING DOCUMENTATION AND OPERATIONAL CONSIDERATIONS

10.1 REGULATORY, ETHICAL, AND STUDY OVERSIGHT CONSIDERATIONS

10.1.1 INFORMED CONSENT PROCESS

10.1.1.1 CONSENT/ASSENT AND OTHER INFORMATIONAL DOCUMENTS PROVIDED TO PARTICIPANTS

Consent forms describing in detail the study intervention, study procedures, and risks will be given to the participant and written documentation of informed consent will be completed prior to starting the study intervention. The following consent materials are submitted with this protocol:

- Study Volunteer Informed Consent Form
- Study Participant Informed Consent Form
- Recruitment Brochure
- Recruitment Flyer
- Early Withdrawal Phone Call Script
- Lost to Follow-Up Phone Call Script

10.1.1.2 CONSENT PROCEDURES AND DOCUMENTATION

At the end of the Pre-screening phone call, all eligible patients will be provided a copy of the consent and HIPAA forms via e-mail. Patients will also be provided an electronic copy of HealthPartners' statement of non-discrimination form. During the Pre-Treatment phone call, research staff will review the consent and HIPAA forms with the patients. Patients will be allowed time to review all documents and ask any questions prior to signing electronically. Research staff will confirm that the patients understand the information in the forms and answer any questions. To obtain signature, the e-consent framework in REDCap will be utilized. This framework allows the patient initials, date, time to be stamped in the footer as extra identity as to who is completing the consent and HIPAA documents. Following the consent conversation, the staff member will sign and e-mail the consent and HIPAA electronically to the patient. The patient will electronically sign, certify, and submit the consent and HIPAA in REDCap. A fully executed PDF copy of the consent and HIPAA will be provided electronically to the patient for their records as well as saved via the auto-archiver function in REDCap. Research staff will complete this process during the Pre-Treatment phone call, to ensure completion and assist if there are any questions.

10.1.2 STUDY DISCONTINUATION AND CLOSURE

This study may be temporarily suspended or prematurely terminated if there is sufficient reasonable cause. Written notification, documenting the reason for study suspension or termination, will be provided by the suspending or terminating party to study participants, investigators, the funding agency, the IRB and regulatory authorities. If the study is prematurely terminated or suspended, the PI will promptly inform study participants, the IRB, and the funding agency and will provide the reason(s) for the termination or suspension. Study participants will be contacted, as applicable, and be informed of changes to the study visit schedule.

Circumstances that may warrant termination or suspension include, but are not limited to:

- 1. Determination of unexpected, significant, or unacceptable risk to participants
- 2. Demonstration of efficacy that would warrant stopping
- 3. Insufficient compliance of study staff to the protocol (ie, significant protocol violations)
- 4. Data that are not sufficiently complete and/or evaluable
- 5. Determination of futility

The study may resume once concerns about safety, protocol compliance, and data quality are addressed, and satisfy the funding agency, IRB, or other relevant regulatory or oversight bodies.

10.1.3 CONFIDENTIALITY AND PRIVACY

Participant confidentiality and privacy is strictly held in trust by the participating investigators, their staff, the safety and oversight monitor(s), and the sponsor(s) and funding agency. This confidentiality is extended to the data being collected as part of this study. Data that could be used to identify a specific study participant will be held in strict confidence within the research team. No personally-identifiable information from the study will be released to any unauthorized third party without prior written approval of the sponsor/funding agency.

All research activities will be conducted in as private a setting as possible.

All study regulatory binders will be stored in a locked file cabinet within a secure office. The internal study monitor, representatives of the IRB, or regulatory agencies, may inspect all documents and records required to be maintained by the investigator, for the participants in this study. The clinical study site will permit access to such records.

The study participant's contact information will be securely stored at the clinical site for internal use during the study. At the end of the study, all records will continue to be kept in a secure location for as long a period as dictated by the reviewing IRB, Institutional policies, or sponsor/funding agency requirements.

Study participant research data, which is for purposes of statistical analysis and scientific reporting, will be password-protected and stored on REDCap, a secure web-based system. Only research study staff will have access to the data. Individual participants and their research data will be assigned a unique study identification number. While the study is active, subject identifiers (e.g. name, MRN) will be stored in REDCap, however, after the study is closed all subject identifiers will be removed.

The PI will ensure all mechanisms used to share data will include proper plans and safeguards for the protection of privacy, confidentiality, and security for data dissemination and reuse (e.g., all data will be

thoroughly de-identified and will not be traceable to a specific study participant). Plans for archiving and long-term preservation of the data will be implemented, as appropriate.

10.1.4 FUTURE USE OF STORED SPECIMENS AND DATA

After the study is completed, the de-identified data will be and stored in REDCap for use in future research. Permission to keep the de-identified data will be included in the informed consent.

10.1.6 SAFETY OVERSIGHT

There is no Data Safety Monitoring Board for this study, as acupuncture has been previously shown to be safe and have minimal risks. During team meetings, the PI and study will review a rolling report of adverse events and report them appropriately.

10.1.7 CLINICAL MONITORING

N/A, refer to next section.

10.1.8 QUALITY ASSURANCE AND QUALITY CONTROL

Study staff will perform internal quality management of study conduct, data collection, documentation and completion.

Quality control (QC) procedures will be implemented as follows:

Informed consent --- Study staff will review both the documentation of the consenting process and 10% of the completed consent documents. Feedback will be provided to study staff to ensure proper consenting procedures are followed.

Source documents and the electronic data --- The majority of data will be directly entered into eCRFs in REDCap. To ensure accuracy for data not directly entered in REDCap, study staff will compare a representative sample of source data against the database, targeting key data points in that review.

Intervention Fidelity — Consistent delivery of the study interventions will be monitored throughout the intervention phase of the study. Procedures for ensuring fidelity of intervention delivery are described in **Section 6.2.1, Interventionist Training and Tracking**.

Protocol Deviations – The study team will review documented protocol deviations on an ongoing basis and will implement corrective actions when the quantity or nature of deviations are deemed to be at a level of concern.

Should independent monitoring become necessary, the PI will provide direct access to all trial related sites, source data/documents, and reports for the purpose of monitoring and auditing by the sponsor/funding agency, and inspection by local and regulatory authorities.

